# 13. ASSESSMENT OF EFFICACY

## 13.1 Data Collection

Data will be collected via the electronic medical record (EMR) or other hospital information system and ICU telemetry systems. Once collected, data will be transferred by study personnel to the Target Health

electronic data capture system, which has been audited by FDA in connection with multiple drug approvals. GCP will be observed throughout. Extensive data not already defined in this protocol will be available for analysis via the EMR and telemetry systems.

## 13.2 Maintenance of Blinding

Investigational drug will be delivered by infusion and labeled by the hospital research pharmacist who is the only unblinded member of the study site. ICU personnel are entirely masked as to treatment assignment, as are patients. Even in the event of unintentional blinding because of differential efficacy of drug and placebo, the randomization scheme prevents staff from knowing the next treatment assignment. Moreover, the primary and declared secondary endpoints are not subject to interpretation by ICU staff.

## 13.3 Intercurrent Events

Given that this is an ICU study, the standard practice is to use the ICH E9 (R1) "treatment policy strategy" where all additional treatments given to the patient are considered to be part of care in both treatment groups. Thus, the analysis does not control for them but rather ignores them. Both remdesivir and dexamethasone will be considered in this way since there are no approved indications for Critical COVID-19. The treatment policy strategy is based on the ICH E9 ITT Principle. Thus, the occurrence of an intercurrent event is considered irrelevant in defining the treatment effect of interest; the value for the variable of interest is used regardless of whether or not the intercurrent event occurs. For example, when specifying how to address use of additional medication as an intercurrent event, the values of the variable of interest are used whether or not the patient takes additional medication. The study further benefits in that study treatment is limited to three days so any subsequent intercurrent event is considered to be part of the treatments being compared. One situation where the treatment policy strategy cannot be implemented for intercurrent events that are terminal events, e.g. going on ECMO or dying since values for the variable after the intercurrent event do not exist; then the estimand based on this strategy cannot be constructed with respect to a variable that cannot be measured due to death or being put on ECMO. Thus, dying or going on ECMO will impose a failure on all time to event outcomes other than survival.

## 13.4 Dropouts

Dropouts are not expected given that this is an ICU study. In the event of dropouts (including early withdrawals), these events will be reviewed at a Biostatistics Data Review Meeting (BDRM) to determine (in a blinded manner) the impact on each efficacy endpoint as well as an alternative impact to be applied in sensitivity analyses. The general approach will be to consider early withdrawals from a best practices perspective; for example, a patient going home on Day 10 who refuses follow-up at Day 28 and Day 60 is likely alive where a patient being transferred to a hospice is to be assumed as dead at Day 28 and Day 60.

## 13.5 Primary Efficacy Endpoint

The original primary efficacy endpoint has changed from a binary composite endpoint originally suggested by the original FDA division to a cumulative distribution of respiratory failure resolution at the suggestion of the study Data Monitoring Committee held July 14, 2020. The DMC counseled the use of a primary endpoint that would use "all the data" available to establish a difference between drug and placebo. The DMC recommended a time series approach, e.g. cumulative distribution, for the time to resolution of respiratory failure, originally a secondary endpoint but elevated to the primary endpoint.

The new primary efficacy endpoint is thus consistent with the recent FDA approval of remdesivir for a less ill study population as informed by recent FDA input (Reference ID: 4613030 NeuroRx, Inc.) in which FDA recommended the cumulative distribution of the time to resolution through Day 28 with concurrent Day 28 survival. The endpoint is further informed by recent FDA guidance not released at the time of study inception.

---

 Statistical Considerations for Clinical Trials During the COVID-19 Public Health Emergency June 2020

## 13.6 Key Secondary Endpoint

Given the recent remdesivir approval and publication, the percents achieving a NIAID Score 6-8 by Day 28/exit (primary) and by Day 60/exit (secondary) will be the key secondary endpoint which was the remdesivir primary efficacy endpoint.

## 13.7 Assessments of Endpoints

### ***Cumulative Distribution: Resolution of Respiratory Failure***

The cumulative distribution will use all randomized and treated patients. Resolution of respiratory failure is defined as no mechanical or non-mechanical ventilation or high-flow nasal O2. Primary endpoint ascertainment requires that recovery from respiratory failure be maintained for at least 7 days without relapse. Patients must survive through Day 28 to be counted as having resolved. Any deaths irrespective of respiratory failure resolution or withdrawals without respiratory failure resolution will be counted as failures at Day 28; only documented resolution events will be counted as success in the distribution construction; this conservative approach is what was done for remdesivir. Imputing Day 28 failure aligns the cumulative distribution curve with the cumulative respiratory failure free days. A 20% absolute advantage is considered to be clinically meaningful.

### ***NIAID 8-point scale***

The NIAID 8-point scale will be used as a measure of recovery from Critical COVID-19. NIAID Scores will be collected daily through hospital discharge and at Day 28 and at Day 60. All on-study deaths (NIAID Score=1) will be carried through Day 28/exit and Day 60/exit. The distribution of the improvement will be assessed relative to the pre-treatment baseline. The percents achieving a NIAID Score 6-8 by Day 28/exit (primary) and by Day 60/exit (secondary) will be of interest from a regulatory and clinical perspective to be consistent with the remdesivir approval.

### ***Survival***

Survival lifetables will be constructed through Day 28 and then through Day 60. Patient death is defined as asystole. Data will be collected on whether the death occurred after withdrawal of care and, if so, the reason for withdrawal of care. Patient death is most likely to occur where the patient was hospitalized. Data will be collected on whether the death occurred after withdrawal of care and, if so, the care withdrawal reason.

### ***Time to Events***

Secondary time to event outcome measures include time to ICU discharge, time on invasive mechanical ventilation (subgroup analysis), time on non-invasive ventilation (subgroup analysis), time to discharge alive, and time to resolution of organ failure through Day 28. In addition, the Day 28 estimate from each lifetable will be analyzed. These endpoints will be displayed and analyzed in the same way as the time to respiratory failure resolution. Any deaths irrespective of an event (all favorable) or withdrawals without the event will be counted as failures at Day 28; only documented events will be counted as success in the distribution construction; this conservative approach is consistent with what was done for remdesivir. Imputing Day 28 failure aligns the cumulative distribution curve with the cumulative event days.

### ***Index of Respiratory Distress***

The PaO2/FiO2 ratio shall be calculated from the continual telemetry data obtained from the ICU information system and arterial blood gas (ABG) for patients while on mechanical ventilation. This variable is not useful after O2 on mechanical ventilation has been reduced because the ratio is reduced even though oxygenation is already improving. In the absence of an arterial line, ABG's will be collected only when medically indicated.

### ***Oxygenation Index***

The Oxygenation index is defined as:

$$OI = \frac{FiO_2 \times M_{PAW}}{PaO_2}$$

### ***Inflammatory Markers***

TNF $\alpha$  and other cytokine studies will be performed by the central lab. Note that these are not declared efficacy or safety endpoints.

### ***Improvement in Chest x-ray***

Chest x-ray images will be collected (1) pre-treatment, (2) 48-96 hours post start of infusion, (3) 1 week  $\pm$ 2 days post start of infusion, and (4) two weeks  $\pm$  2 days post start of infusion, provided the patient is still hospitalized. All x-rays will be read by a blinded radiologist panel and scored according to the Rapid Assessment of Lung Edema (RALE) score (Warren 2017).

### ***Clinical decision to terminate mechanical ventilation***

Study research personnel will collect all available data regarding the clinical decision-making that guides removal mechanical ventilation in relation to clinical deterioration or lack of clinical response (e.g. change in status to comfort measures, poor prognosis for recovery, allocation of resources in a pandemic setting, etc.).

### ***Additional data to be collected***

Because of the unique nature of this study and the circumstances under which it is being conducted, at FDA's request, sponsor will collect all data regarding the use of experimental therapeutic agents (e.g. hydroxychloroquine, IL-6 inhibitors, and other topics of interest) and deliver those data to FDA for further analysis. Sponsor will make this analysis data set available to the broader scientific community as well.

## **13.8 Patient Follow-up Strategies**

This study begins with the patients in the ICU and could end with the subject still in the ICU, in another hospital, at home, or deceased. Every possible effort has been taken to minimize dropouts and losses to follow-up. The following actions have been taken to ensure follow-up:

1. encourage sites to establish reliable follow-up networks with patients for use post discharge.
2. follow an algorithm that includes multiple communication/information gathering strategies to starting with 3 documented telephone calls, followed by fit for purpose use of text messages, email, next of kin/contact person outreach, review of system medical records as appropriate, primary physician follow up, public records and, again if appropriate, locator services.

Thus, we expect the loss to follow-up in this study to be quite low.

## **14. STATISTICAL ANALYSIS**

### **14.1 Statistical Design and Analyses**

All analyses will be pre-specified in a Statistical Analysis Plan to be finalized with FDA prior to database lock.

A group sequential design will be employed with one interim analyses for safety and futility (n=21) and a second interim analysis for safety and futility (n=81). At the request of FDA, the efficacy look was dropped prior to conducting the n=81 evaluation.

All calculations will be performed using SAS statistical software, version 9.3 or later, and StatXact, version 10 or later. All efficacy and safety data will be displayed in tables and listings separately for each treatment group. Post-Text TLFs will be provided in collated electronic MS Word .rtf files (i.e. table columns and rows appear in MS Word Table format).

The statistical analyses of the study will be conducted in a GCP environment (ICH E6).

There will be an independent statistical reporting group (ISRG) responsible for conducting all analyses; there will be separate unblinded biostatistician supporting the DSMB and a blinded biostatistician

responsible for any protocol modifications.

All patient data will be collected via the electronic medical record and in-house ICU telemetry systems. Dedicated research personnel will extract data to a de-identified study database for statistical analysis.

## 14.2 Sample Size Calculation

The sample size calculation of 198 subjects (2:1 allocation favoring the RLF-100 group) is required to detect a 22% absolute increase in the percent achieving respiratory failure resolution favoring the RLF-100 group (assuming 50% success) and the SOC group (assuming 40% success) with 81% power and two-sided overall 5% Type 1 error accounting for the group sequential design using the method in Schoenfeld. This degree of efficacy corresponds to a 0.52 hazard ratio.

## 14.3 Study Populations

The intent-to-treat (ITT) population will be based on all randomized patients receiving any study treatment. ITT will be analyzed as randomized.

The safety population will be based on all randomized patients receiving any study treatment. Safety will be analyzed as treated.

The modified intent-to-treat (mITT) population will exclude untreated patients as well as ineligible patients; this will be the primary efficacy population. The primary analysis set will not condition on any post-randomization outcomes.

In the event that >5% of the mITT population experience a major protocol deviation that impacts the primary efficacy endpoint, such cases will be excluded and a Per Protocol (PP) population will be constructed and the primary efficacy endpoint analyses will be repeated for the PP population. A BDRM will be held to review and to determine such major deviations which would make it difficult to evaluate the study therapy, e.g. going on an approved Critical COVID-19 therapy (none currently exist) or premature withdrawal from study. The BDRM will be conducted at study completion to determine final mITT and PP population membership.

## 14.4 Statistical Methods

The primary analyses will be based on the modified intent-to-treat (mITT) population.

All analyses will be conducted according to the treatment policy strategy to handle intercurrent events. In the event of any dropouts, the BDRM will discuss how to best count these patients in the primary analysis and then in a sensitivity analysis.

Evaluation of the primary efficacy endpoint (cumulative distribution through Day 28) will be analyzed by a pre-defined proportional hazard model to include age (<65,  $\geq$ 65 years), baseline NIAID score (2,  $>$ 2), RDR (<150 mmHg,  $\geq$ 150 mmHg), previous anti-viral therapy for COVID-19 (none, any), and study treatment as covariates (primary); the proportional hazard model will be used to estimate unbiased treatment effects while controlling for these four baseline covariates. To count in the accruing numerator, the event must be confirmed by the site to last for at least 7 days with Day 28 survival. SAS PROC PHREG will be used for these analyses. See Sections 13.3-4 for rules to count respiratory failure resolution and the handling of intercurrent events and dropouts.

The key secondary efficacy endpoint will be the percent achieving a NIAID Score 6-8 by Day 28/exit (primary) and by Day 60 (secondary) and will be analyzed by comparing success percents. Patients who die or withdraw will not be counted as achieving success (event). The primary analysis will be a logistic regression model containing the same covariates as the primary efficacy endpoint. The percents achieving success by Day 28/exit will also be compared using a two-sided Fisher Exact test.

The survival curve will be displayed using Kaplan-Meier lifetables to account for censoring in the estimation of the Day 28 and Day 60 survival outcomes; Greenwood's formula will be used to estimate Day 28 outcomes with two-sided 95% confidence intervals constructed to compare the treatment group differences. The same proportional hazard model as for the primary efficacy endpoint will be used to analyze survival; in addition, an unstratified log rank test will be performed.

The other time to (favorable) event outcomes will also be assessed using cumulative distributions through Day 28 with an additional evaluation at Day 28; these outcomes include the time to ICU discharge, time on invasive mechanical ventilation, time on non-invasive ventilation, time to discharge alive, and time to resolution of organ failure. These endpoints will be analyzed and displayed the same way as the time to respiratory failure resolution with the exception of just through Day 28. Two-sided 95% confidence intervals will be displayed for the Day 28 success rate differences in the same manner as for the key secondary efficacy endpoint. Any deaths or placement on ECMO on or before Day 28, irrespective of an earlier favorable event, or withdrawals without the favorable event ever occurring will be counted as failures at Day 28; only documented favorable events will be counted as success in the distribution construction and the denominator will include all mITT patient per treatment group. The Day 28 failure imputation allows the cumulative distribution to align with the calculation of mean days saved; thus, patients withdrawing earlier than Day 28 or not reaching a favorable event by Day 28 will be counted as failures at Day 28 in the construction of the time to event lifetables; this is consistent with how favorable events were handled for remdesivir. See Sections 13.3-4 for the handling of intercurrent events and dropouts.

The mean NIAID score will further be displayed over time. The area under the curve will also be calculated and compared using an unpaired t-test. Patients dying prior to Day 28 (then Day 60) will be carried through Day 28 (then Day 60) as being dead (NIAID=1).

The NIAID score will further be assessed for the change from baseline to Day 28/exit and then to Day 60/exit. A mixed model repeated measures (MMRM) containing the same covariates as the primary efficacy endpoint will be performed to explore the impact of modeling serial data; an unstructured covariance symmetry will be assumed; in the event that the unstructured covariance structure does not converge, then an autoregressive (1) structure will be tried, and if that does not work, then a Toeplitz structure will be tried.

Other continuous variables, e.g., blood pressure, respiratory rate, tidal volume, organ function measurements will be summarized by mean  $\pm$  standard deviation, median, and range. Categorical variables, e.g., lung injury score, chest X-ray findings, will be summarized by frequency and corresponding % incidence.

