Dosage, Route of Administration, and Schedule:	Three escalating doses of RLF-100 (Aviptadil): 50, 100, and 150 pmol/kg/hour or placebo administered over 12 hours via IV infusion on successive days. If side effects cannot be managed with ICU protocol, dose reduced or halted.
Statistical Methods:	Primary endpoint (cumulative distribution of the time to respiratory failure resolution) with concurrent survival through Day 28 will be displayed by a lifetable through Day 28 and analyzed using a proportional hazard model analysis containing 4 pre-defined baseline covariates and randomized treatment group (primary) as well as an unstratified log rank test (secondary). Primary endpoint ascertainment requires that recovery from respiratory failure be maintained for at least 7 days without relapse. The cumulative distribution will be constructed through Day 28 with no censoring for death or withdrawal; such patients will be regarded as failures. Other time to event outcomes will be similarly analyzed with the exception of survival which will censor for any withdrawals. NIAID Score will be analyzed by carrying forward any early deaths through Day 28; other ordinal and continuous outcomes will be assessed by mixed model repeated measures through Day 28. The primary analysis will be based on the modified intent-to-treat (mITT) population to be based on all treated patients.

Sample Size Calculation:	For the primary efficacy endpoint, assuming a 40% success percent in the placebo group by Day 28 and a 62% success percent in the RLF-100 group by Day 28, for log rank test with two-sided overall 5% Type I error and 81% power, the sample size to detect a 22% absolute improvement in the percent achieving respiratory failure resolution by Day 28 (from 40% to 62%) is 198 subjects in the primary analysis group (2:1 randomization favoring the RLF-100 group). A 20% absolute advantage in the percent achieving respiratory failure resolution by Day 28 is deemed to be clinically meaningful.
Interim Analyses	An interim look for safety and futility will be conducted once the first 21 randomized subjects complete Day 7. A second interim look for safety, futility, and efficacy will be conducted once the next 81 subjects complete Day 28 but the study will not be prematurely stopped for efficacy.

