## 10.8 Randomization Procedures

Randomization will be on a 2:1 basis with a random block size of 3 or 6; a centralized randomization will be used. Subjects will be stratified according to RDR ( $<200$  mmHg,  $\geq 200$  mmHg) and previous anti-viral therapy for COVID-19 (none, any).

Using this method, even if site personnel believe they can tell the difference between clinical reaction to RLF-100 vs. placebo, they have no possibility to guess what the next allocation will be.

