### 15.3 Primary Efficacy Endpoint: Time to Respiratory Failure Resolution

The primary outcome measurement is the cumulative distribution which shows when resolution occurs for

each treatment group. Resolution must last for at least 7 days and start by Day 28; patients must be alive on Day 28. In accordance with the treatment policy strategy, deaths and going on ECMO during the first 28 days are counted as failures; they are counted in the Day 28 denominator to permit the area under the curve to correspond to event-days saved. The mITT patients per treatment group are the respective denominators. The data will be analyzed using a pre-defined proportional hazards model (primary) and unstratified log rank test (secondary); the hazard ratio and two-sided 95% confidence interval will be the critical statistics; in addition, a two-sided 95% confidence interval will be computed for the Day 28 outcome. A 20% absolute improvement in the Day 28 success rate is deemed to be clinically meaningful. A 40% success rate is expected for Placebo + Maximal SOC while a >50% success rate is expected for RLF-100 + Maximal SOC.

Sensitivity analyses are also planned; see Section 13.4. The BDRM will consider the most likely outcome on a patient-by-patient basis. However, a tipping point analysis using the proportional hazard model will be performed where all RLF100-1 patients dropping out will initially be considered as failures while all placebo patients will initially be considered to be successes. The two-dimensional tipping point analysis will shift the balance over the spectrum of all independently being successes and all being failures.

The mITT population will be used for the analysis.

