## **15.4 Key Secondary Efficacy Endpoint: Exit NIAID Score Reaches 6-8**

The key secondary outcome measurement is the change in NIAID Score from pre-treatment baseline through Day 28/exit (then Day 60/exit). Deaths are carried forward using NIAID Score=1 while, for withdrawals, the last value before Day 28 (60) is used for the Day 28 (60)/exit outcome. The denominator is fixed per treatment group. The data will be analyzed using a pre-defined logistic regression model (primary) and Fisher Exact test (secondary); the proportion achieving NIAID Score 6-8 by Day 28/exit (primary) and by Day 60/exit (confirmatory) will be presented as the key summary measure to be estimated from the lifetable. A 20% absolute improvement in the Day 28 (and Day 60) percent is deemed to be clinically meaningful. A 40% success rate is expected for Placebo + Maximal SOC while a >60% success rate is expected for RLF-100 + Maximal SOC.

The same two-dimensional tipping point analysis will be conducted as for the primary efficacy analysis except using a logistic regression model.

In addition, a MMRM model using the same covariates will be run for the change from pre-treatment baseline to Day 28/exit using the same baseline covariates for the primary efficacy endpoint. The mean change from pre-treatment baseline to Day 28/exit will be the endpoint of interest. The analyses will be repeated at Day 60/exit (confirmatory). The MMRM model will use an unstructured covariance symmetry will be assumed; in the event that the unstructured covariance structure does not converge, then an autoregressive (1) structure will be tried, and if that does not work, then a Toeplitz structure will be tried. The mean change from pre-treatment baseline to Day 28/exit (primary) and Day 60/exit (confirmatory) will also be of interest.

The mITT population will be used for these analyses.

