## **15.5 Secondary Efficacy Endpoints: Time to Favorable Events**

These secondary efficacy endpoints will be analyzed in the same manner as the primary efficacy endpoint. For each such endpoint, the outcome measurement is the cumulative distribution which is a figure that shows when the favorable event occurs for each treatment group. Any deaths or placement on ECMO on or before Day 28, irrespective of an earlier favorable event, or withdrawals without the favorable event ever occurring will be counted as failures at Day 28; only documented favorable events will be counted as success in the distribution construction and the denominator will include all mITT patient per treatment group. The Day 28 failure imputation permits the area under the curve to correspond to event-days. The denominator is fixed per mITT treatment group. To count in the accruing numerator, the event must be confirmed by the site to last for at least 7 days. The data will be analyzed using the same pre-defined

proportional hazards model (primary) and an unstratified log rank test (secondary); the hazard ratio will be the critical statistic.

The mITT population will be used for the analysis.

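### RDR is split at 200 mmHg for randomisation but at 150 mmHg in the models, so the RDR stratum as randomised is in no analysis, and the log-rank tests use neither randomisation factor

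*Combined protocol and SAP*

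**What the plan says.** **Allocation.** Section 10.8 uses central 2:1 randomisation in blocks of 3 or 6: "Subjects will be stratified according to RDR", cut at 200 mmHg, and by previous anti-viral therapy (none, any).

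**Primary model.** Section 14.4 specifies a proportional hazards model with age, baseline NIAID score, RDR below 150 mmHg or not, and then the terms quoted here: "150 mmHg), previous anti-viral therapy for COVID-19 (none, any), and study treatment as covariates (primary".

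**Models that reuse this set.**
- Key secondary endpoint (14.4): "The primary analysis will be a logistic regression model containing the same covariates as the primary efficacy endpoint".
- NIAID change from baseline (14.4): "A mixed model repeated measures (MMRM) containing the same covariates as the primary efficacy endpoint will be performed". Section 15.4 repeats this.
- Survival (14.4, 15.6) and the other time-to-event endpoints (14.4, 15.5) use the same proportional hazards model.
- The PaO2/FiO2 ratio (15.9) and the oxygenation index (15.10) inherit it by reference.

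**Log-rank tests.** The synopsis adds to the primary model "as well as an unstratified log rank test (secondary"). Sections 14.4, 15.3, 15.5 and 15.6 also call the test unstratified.

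**The concern.** An analysis should normally account for the factors that constrained the randomisation. Stratified blocks balance the arms within each stratum. If the stratum predicts outcome and the analysis leaves it out, the model-based standard error is too large for the design: the test becomes conservative and power is lost.

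Here one randomisation factor enters the models exactly as randomised and the other does not. A patient with RDR from 150 to 199 mmHg is in the low group for allocation and in the high group in the model. RDR is still partly adjusted for, because the 150 mmHg indicator is correlated with the 200 mmHg stratum. The unstratified log-rank tests account for neither factor. At stake are some efficiency in the primary and key secondary analyses and an unexplained discrepancy in the definition of the primary model.

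**Working it through.** **1. The text side by side**

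| Factor | Randomisation (10.8) | Covariate-adjusted models (14.4 and those reusing it) | Log-rank tests |
|---|---|---|---|
| RDR | 200 mmHg | 150 mmHg only | not used |
| Previous anti-viral therapy | none, any | none, any | not used |

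**2. The plan's power figure, as a base.** Inputs (synopsis, 10.7, 14.5): 40% versus 62% success by Day 28, 66 placebo and 132 RLF-100 patients, two-sided 5%, 81% power. Comparing the two proportions gives 82.3% power by Fisher's exact test and 79.8% with a continuity correction, which brackets 81%. By the Schoenfeld log-rank formula:
- hazard ratio = ln 0.60 / ln 0.38 = 0.528 (14.2 states 0.52)
- expected events = 66 × 0.40 + 132 × 0.62 = 108.2
- power = Φ(√(108.2 × 1/3 × 2/3) × |ln 0.528| − 1.96) = Φ(1.17) = 88.0%

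The sample size is not in dispute here. The calculation shows that a time-to-event analysis at these rates starts above 81%.

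**3. Patients who change RDR group.** The documents do not give the RDR distribution, so I assume a normal one with mean m and SD s. The share at 150 to 199 mmHg is Φ((200 − m)/s) − Φ((150 − m)/s).
- m = 150, s = 60: 29.8%, or 59 of 198
- m = 190, s = 60: 31.4%, or 62 of 198
- over m = 120 to 220 and s = 40 to 80: minimum 19.5% (120, 80), maximum 46.8% (175, 40)

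**4. Power by simulation.** Trials of 198 patients, with 2:1 blocks of 3 or 6 within the four strata, exponential times censored at Day 28, and marginal Day 28 rates calibrated to 40% and 62%. Assumed: 60% prior anti-viral use with no effect; age and NIAID split 50:50, each with a log hazard ratio of size 0.5; RDR effect linear (0.5 per SD), a step of 1.0 at 200 mmHg, a step of 1.0 at 150 mmHg, or none. There were 10,000 trials per setting for the first two distributions and 6,000 for the other three. The Monte Carlo standard error of a power difference is 0.1 to 0.3 points.

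The planned Cox model has 86% to 92% power. Change in power, in points, from adding the 200 mmHg stratum to it:

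| RDR mean/SD | Linear | Step at 200 | Step at 150 | No effect |
|---|---|---|---|---|
| 150/60 | +0.65 | +2.82 | +0.02 | −0.05 |
| 190/60 | +1.09 | +2.78 | 0.00 | −0.07 |
| 120/40 | +0.12 | +0.42 | −0.05 | 0.00 |
| 175/40 | +0.92 | +3.20 | +0.25 | +0.12 |
| 220/80 | +0.50 | +2.55 | +0.08 | −0.05 |

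In the 120/40 row only about 5 of 198 patients have RDR of 200 or above: 198 × (1 − Φ(2)) = 4.5.

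Other changes over the same settings:
- key secondary logistic model with the stratum added: 0.0 to +0.8 (linear), +0.4 to +2.1 (step at 200), −0.1 to +0.2 (step at 150), 0.0 to +0.2 (none)
- log-rank test stratified by both factors instead of unstratified: −0.5 to +3.0
- 200 mmHg replacing 150 mmHg in the Cox model: −4.5 to +3.4

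**5. Type I error** (40% in both arms; standard error 0.2 to 0.3 points). Planned Cox 4.5% to 5.3%; with the stratum added 5.0% to 5.6%; unstratified log-rank 3.9% to 5.4%; stratified log-rank 4.7% to 5.5%.

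**6. Cross-checks.** Two further simulations at mean 150, SD 60 (2,500 trials per setting) gave +0.8 and +1.0 (linear), +2.4 in both (step at 200), +0.1 and +0.2 (step at 150), and −0.1 and 0.0 (no effect). Another set with different assumptions compared a 200 mmHg term with a 150 mmHg term, with the RDR effect acting at 200. The gain was about 0 to 3 points for RDR hazard ratios up to 2.5 and about 5 points at 4. At 4 the unstratified log-rank test rejected in only 2.5% to 3.0% of null trials.

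**The case against.** The strongest reply is that no harm is demonstrated. Type I error is controlled, the planned model exceeds 81% power in these simulations, and the 3-point gain needs a step at exactly 200 mmHg with a hazard ratio of about 2.7, which nothing in the documents supports. That is fair, and it keeps the point minor. Nor is 3 points an upper bound, since a stronger RDR effect gives more.

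One of the two cuts may simply be a typing error. If allocation in fact used 150 mmHg, the stratum is already in the model and Section 10.8 is what needs correcting. This stands, and the fix begins there.

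An unstratified log-rank test is also a defensible simple companion to an adjusted primary model. That is so, and it can be kept as supportive.

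The remedy also reaches endpoints that were not simulated: survival, the mixed models, and the ventilation endpoints restricted by Section 15.1 to patients initially on that support. In a rough run with an assumed subgroup of 70 and no RDR effect, the stratified log-rank test lost about 1 point (38.1% to 36.8%), close to simulation noise. Finally, part of the gain from adding the stratum may come from a less conservative test.

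None of this explains why one randomisation factor is carried into the models as randomised and the other is not.

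**Conclusion.** The discrepancy is real on the current text. RDR is split at 200 mmHg for allocation and at 150 mmHg in every covariate-adjusted model, the RDR stratum as randomised is in none of them, and the log-rank tests use neither factor. The severity is minor: the consequence is a slightly conservative analysis, not a false-positive risk. The loss in the primary Cox analysis is about 3 points of power if prognosis follows the 200 mmHg grouping at the assumed strength, about 1 point or less if it is linear, and essentially nil otherwise. Confidence in the mismatch is high. The sizes depend on the assumed RDR distribution and effect, which the documents do not give.

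**What to change.** 1. Confirm which RDR cut the central randomisation system used, and make Sections 10.8 and 14.4 consistent with it.
2. If it was 200 mmHg, keep the four pre-defined covariates in 14.4, including RDR at 150 mmHg, and add the RDR stratum as randomised. Together they form a three-level term: below 150, 150 to 199, and 200 or above. Use this set in every model that reuses the primary covariates. Do not replace 150 with 200, since that could cost up to 4.5 points of power.
3. Stratify the secondary log-rank tests by the two randomisation factors, and keep the unstratified version as supportive.
4. State why 150 mmHg was chosen.

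**Cost.** SAP wording only, because the stratum is recorded at randomisation. The Cox model gains one parameter, with a power change of −0.1 to +0.3 points if the 200 mmHg stratum is not prognostic. Simulated type I error moves from 4.5–5.3% to 5.0–5.6%. The stratified log-rank test may lose up to 0.5 points at 198 patients if RDR is not prognostic or few patients have RDR of 200 or above, and perhaps more in small subgroups. It is a late change to a pre-defined model: Section 14.5 reports that the 81-patient futility analysis has been conducted. The blinded biostatistician described in Section 14.1 should therefore document it, and it should be settled in the SAP to be finalised with FDA before database lock.
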